9.3 Analysis sets

Participants that violate the protocol are excluded from the Per-Protocol Analysis Set. Protocol violations involve:

- not fulfilling criteria for inclusion and exclusion
- major deficiencies / discrepancies in the completion of questionnaire 1.
- non-adherence to pre-specified timelines.
- any concomitant vaccinations and other potential confounder that may interfere with the reactogenicity under study, or with the interpretation of the data.

As the electronic questionnaires enforce most criteria above, in the majority of cases decisions to exclude from the PPA data set are done automatically.

9.4 Descriptive statistics

Descriptive characteristics will be presented per study group, as numbers and/or proportions of children with an applicable parameter per group. The results will be displayed per group. For continuous variables, data will be presented as mean \pm SD (confidence interval) and proportions, and median (range). For binary variables data will be presented as n/N (%), and 95% CI. The secondary endpoints will only be descriptively analysed.

9.5 Comparability of study groups

Both study groups should be comparable for baseline characteristics and potential confounders, as defined in Chapter 5.

9.6 Statistical methods for data analysis

The primary endpoint of the study, fever cases observed within 4 days after vaccination will be analyzed using logistic regression with vaccination groups ("old" / "new" product) and potential confounders as listed in 5.3 as explanatory factors, applying a log link in order to obtain relative risk estimates at the end. Relative risk and its 95% CI of occurrence of fever cases with the "new" and "old" NeisVac-C® product will be calculated from the regression model assessing a potential increase of fever reactions with the "new" product. If the upper limit of the 95% CI is below 1.5 then the "new" product is considered to be non-inferior to the old one as far as fever reaction is concerned.

The secondary endpoints will be analyzed similarly and descriptive without the non-inferiority considerations.

CHAPTER 10. SAFETY REPORTING

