3.1 Study design

This is a non-interventional, open observational non-inferiority study with two cluster- assigned cohorts .

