6.3 Assessments / collection of data

6.3.1 Preregistration and registration

Upon receipt of the first letter parents may pre-register for the study by reporting their email address and scheduled vaccination date. At this date, Lareb will send them an email with a link enabling the parents to register for the study.

After vaccination, parents are given a flyer with information about the study, and how to sign-up for the study (web address and study specific access code).

The following data are requested.

- general data

1. are MenC and MMR vaccines administered both? If only one, or more than 2, vaccines were given, the child cannot further participate.
2. reporting code
3. date of vaccination
4. batch numbers of administered vaccines (to be recorded at baby clinic)
5. injection sites of administered vaccines (arm/leg/left/right) (to be recorded at baby clinic)
6. registration of email address. Per email address, only one child can participate. For more children in a household/family (twins, triplets,..) separate email addresses are required.
7. accept Lareb privacy rules yes/no. Only proceed if ticked: yes.

- data of reporting parent and child

1. confirm email address
2. child: date of birth
3. child: sex
4. child: height at time of vaccination
5. child: weight at time of vaccination
6. baby clinic: place and street address (choose from list).

- base line data

1. medical history, did your child have: ... (tick if applicable)
 - infections,
 - coughing/dyspnea,
 - skin rash,
 - hypersensitivity or allergy,
 - vomiting and/or diarrhea,
 - other: please specify ...,
 - none of the above.

- concomitant medication

1. Does your child use any medication: if yes: specify the medicine, dose, start date and stop date if applicable

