7.4 Product shipment, accountability

All baby clinics in the study region will receive only one batch of NeisVac-C® during the course of the study (one year). Any next shipment to a baby clinic should ensure that the right batch is delivered. From these shipments, also children who do not participate, will receive their NeisVac-C® vaccinations.

For MMR vaccine, there is no preference for particular batches to be used per clinic.

Throughout the study period, the baby clinics will be (re)supplied regularly (every 2-3 months).

Accountability is not a requirement for this study. However, the number of doses per baby clinic is recorded as part of the usual administration and surveillance of the NIP.

It may occur rarely that vaccines from one baby clinic are transferred to another. Therefore we verify the batch numbers by asking the parents.

CHAPTER 8. STUDY GROUPS, RANDOMISATION AND (UN-) BLINDING

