8.2 Randomization and stratification

Central randomisation: baby clinics are randomly assigned to use either the old or the new NeisVac-C®. Shipments are done according to a distribution list, generated to randomly assign either batch to any participating baby clinic, to ensure that both groups are similar in size, and that local differences in confounding factors (e.g. concurrent infections, habits and attitudes towards vaccinations, ...etc) are balanced out.

RIVM/DVP will generate the distribution list, and will provide the baby clinics accordingly (Appendix 2).

8.3 Study size and recruitment population.

In order to evaluate 1215 children per group according to protocol (see paragraph 9.2) we need to recruit higher numbers of children. The following estimations are done to determine the population size to target for participation. With 1215 per group we need 2430 fully evaluable and complete datasets. We assume that 90% of data from an estimated 2700 respondents that have completed all questionnaires are evaluable. We assume that after starting the questionnaires 75% of responders will also complete the last questionnaire, thus giving an estimation of 3600 responding parents that start and agree to participation. Experience of RIVM indicates that about 40% of parents participate to a similar questionnaire proposal. However, to be sure to include the desired number of respondents we assume a lower percentage: 15-20%. Thus we assume that 18.000 to 24.000 parents need to be addressed for taking part in the investigation. In addition, to compensate for other interferences or loss, we intend to address 25.000 parents.

8.4 (Un) blinding procedure

Not applicable

CHAPTER 9. STATISTICS

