9.2 Sample size calculation

For a non-inferiority approach the following assumptions and choices were made:

- null hypothesis: group A receiving the new product, has a higher prevalence of fever than children in group B. The risk ratio between group A and B is 1.5 or more.
- alternative hypothesis (one-sided): the risk ratio between group B and group A is less than 1.5.
- study groups equally sized (approximately)
- type 1 error alpha: rejection null hypothesis when it is actually true, is set at 0,025, one-sided (ICH E9)
- type 2 error beta: rejection null hypothesis, is set at 0,80
- clinically acceptable or meaningful difference between endpoints in group A and group B: risk ratio of 1.5 indicating a higher risk of fever in group A (corresponding with a fever prevalence of 9% in group A).
- sample size is calculated to obtain numbers needed for the Per Protocol Analysis set.

Prior data indicate that the prevalence of fever among the reference group B is about 6%. Sample size was calculated using a web-based sample size calculator Sealed Envelope, based on Blackwelder. We will need to study 1215 children in each group to be able to reject the null hypothesis that the fever rates between in group A are higher than in group B, with probability (power) of at least 0,8. The type I error probability associated with this test of this null hypothesis is 0,05 (two-sided, 0.025% one-sided). If there is truly no difference in fever prevalence between the two groups, then 2430 children are required to be 80% sure that the upper limit of a one-sided 97.5% confidence interval (or equivalently a 95% two-sided confidence interval) of the risk ratio will exclude a difference in favour of the reference group of more than 3%.

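### Baby clinics are randomised, but neither the primary model nor the sample size accounts for clinic, so the interval behind the 1.5 rule is too narrow if reported fever is correlated within clinics

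*Protocol*

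**What the plan says.** **Allocation.** Section 3.1 calls this a "non-interventional, open observational non-inferiority study with two cluster- assigned cohorts". Section 8.2 says that "baby clinics are randomly assigned to use either the old or the new NeisVac-C" vaccine, and sections 7.1 and 9.1 also have clinics randomised. Under section 7.4, "All baby clinics in the study region will receive only one batch of NeisVac-C® during the course of the study (one year"), with transfers between clinics expected only rarely. Product is therefore essentially nested in clinic.

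**Differences between clinics.** Section 8.2 expects random assignment to ensure that "local differences in confounding factors (e.g. concurrent infections, habits and attitudes towards vaccinations, ...etc) are balanced out".

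**Primary analysis.** Section 9.6: "The primary endpoint of the study, fever cases observed within 4 days after vaccination will be analyzed using logistic regression with vaccination groups" and the section 5.3 covariates (gender, weight, length, medical history, household size, daycare), on a log link. The relative risk and its 95% CI come from this model, and non-inferiority is declared if the upper limit is under 1.5. Clinic is not a term in the model, and no random effect, GEE or robust variance is mentioned.

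**Sample size.** Section 9.2 asks for 1215 children per group with 6% fever in both groups, one-sided alpha 0.025 and 80% power, and adds that "sample size is calculated to obtain numbers needed for the Per Protocol Analysis set". Section 8.3 inflates for evaluability, completion and response only. Neither section gives an ICC, a clinic size or a design effect.

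**Data.** Registration (section 6.3.1) already records "baby clinic: place and street address (choose from list").

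**The concern.** When whole clinics are allocated, the product effect is a contrast between clinics, and its standard error has to include between-clinic variation. Randomising clinics removes systematic bias from "local differences in confounding factors" on average. It does not remove the extra variance they cause. A model that treats children as independent leaves that variance out.

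The endpoint is open to such variation. Section 6.5 has temperature taken only when parents suspect fever, so local infections and local habits of noticing and reporting can both affect it.

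The whole safety conclusion rests on one confidence limit. If the interval is too narrow, the error runs in one direction: non-inferiority of the new product is declared more often than the stated 2.5% when the true risk ratio is 1.5.

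**Working it through.** **Inputs from the protocol.** 1215 per group (2430 in total), fever 6% in both groups, margin RR 1.5 or 3 percentage points, one-sided alpha 0.025, power 0.80 (section 9.2).

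**Assumptions, not in the protocol text.** 50 to 200 clinics of equal size and ICC 0.002 to 0.02. Appendix 2 (the distribution list) is named, but its content is not in the text at hand.

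**Step 1: the plan's own figure.** The Blackwelder-type formula on the difference scale gives

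n = (1.96 + 0.8416)² × 2 × 0.06 × 0.94 / 0.03² = 984 per group, not 1215.

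On the log risk-ratio scale, which the section 9.6 rule uses,

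n = (1.96 + 0.8416)² × 2 × 0.94 / 0.06 / (ln 1.5)² = 1496 per group.

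The figure of 1215 is therefore not reproduced by the named method. Both formulas assume independent children.

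**Step 2: design effect and one-sided error.** With m = 2430 / number of clinics,

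- DE = 1 + (m − 1) × ICC
- the true standard error is √DE times the naive one
- one-sided error of the naive rule at RR 1.5 = Φ(−1.96/√DE).

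**Step 3: power of a correct analysis on the risk-ratio scale.** The naive standard error of log RR is √(2 × 0.94 / (0.06 × 1215)) = 0.1606. Power = Φ(ln 1.5 / (0.1606 × √DE) − 1.96). With DE = 1 this is Φ(2.525 − 1.96) = 71%.

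| Clinics | m | ICC | DE | √DE | Error, naive CI | Power, correct SE |
|---|---|---|---|---|---|---|
| any | – | 0 | 1.00 | 1.00 | 2.5% | 71% |
| 200 | 12.15 | 0.002 | 1.02 | 1.01 | 2.6% | 70% |
| 100 | 24.3 | 0.01 | 1.23 | 1.11 | 3.9% | 62% |
| 50 | 48.6 | 0.02 | 1.95 | 1.40 | 8.0% | 44% |

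Middle row in full: DE = 1 + 23.3 × 0.01 = 1.233; √DE = 1.110; error = Φ(−1.765) = 3.9%; power = Φ(0.4055/0.1783 − 1.96) = Φ(0.314) = 62%.

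Unequal clinic sizes would raise the design effect further.

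**Step 4: what clustering accounts for.** The drop from the stated 80% to 71% arises with independent children, because the 3-point difference used for sizing and the risk-ratio rule are on different scales. Clustering accounts only for the further drop, from 71% to 62% in the middle case.

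**The case against.** **The effect may be negligible.** Enrolment runs for a year and the fever window is four days. With 12 to 49 evaluable children per clinic, that is about one to four a month, so few would share an infection wave. This argues for a low ICC from infections. It does not cover persistent local habits of measuring and reporting, and the protocol offers nothing to show that the ICC is near zero. The 8.0% end needs 50 clinics, or 500 invited families per clinic out of the 25,000 in section 8.3, and nothing in the document supports a clinic count that low in particular. This stands as a limit on the size of the point, not on the omission.

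**1215 may contain slack.** 1215/984 = 1.235, close to the middle-case design effect. A reader might infer a hidden cluster allowance. The protocol says nothing of the kind, and on the scale of the decision rule 1215 is already below 1496. The opposite inference, that 1215 demonstrably came from a formula for individually randomised children, is not supported either, because the figure is not reproduced. What can be said is that no allowance is stated.

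**Recruitment may exceed the minimum.** 25,000 × 0.15 × 0.75 × 0.90 = 2531 evaluable, or 3375 at 20% response. This would recover some power but does not repair the interval. With 3375 children in 100 clinics at ICC 0.01, m = 33.75 and DE = 1.33, so the error of the naive rule rises to Φ(−1.96/√1.3275) = 4.4%.

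**A SAP may add clustered errors.** It may. But section 9.6 does not leave the matter open: it states the model, the source of the interval and the decision rule.

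**Conclusion.** The omission is certain on the text: clinics are randomised, product is essentially nested in clinic, the primary model ignores clinic, and no design effect is stated for the sample size.

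The consequence is conditional. The interval is too narrow, and the one-sided error above 2.5%, if within-clinic correlation of reported fever is positive. Section 8.2 makes that plausible but does not establish it. The size cannot be derived from the document. Under the assumed 50 to 200 clinics and ICC 0.002 to 0.02, the error is about 2.6% to 8.0%, from negligible to material, and power on the risk-ratio scale about 70% to 44%.

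Two stronger readings are tempting and are not supported. One is that the interval is known to be too narrow by a given amount; that needs an ICC and a clinic count which the text does not give. The other is that clustering explains the whole shortfall from 80% power; the part from 80% to 71% is the separate scale problem.

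The point still needs correcting before analysis, because the stated error rate of the only confirmatory claim should not depend on an unstated assumption that the ICC is zero.

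**What to change.** **Section 9.6.** Base the relative risk, its 95% CI and the 1.5 rule on a log-link model that accounts for baby clinic. Modified Poisson GEE with clinic as cluster and robust standard errors would serve, as would a clinic random effect. Add a small-sample correction if clinics are few.

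**Section 9.2.** State the number of clinics, an assumed ICC with its basis, and the power after the design effect on the risk-ratio scale used for the decision. If that power is unacceptable, a larger evaluable sample is needed. Rewording alone will not restore it.

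**Cost.** No new data, since clinic is already recorded at registration. The interval will be somewhat wider and the stated power lower.

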10.1 Definitions

All symptoms, reported by the parents occurred during the study period will be considered as adverse event.

A *Serious Adverse Event* (SAE) is any untoward medical occurrence or effect that at any dose:

- results in death
- is life-threatening (at the time of the event)
- requires hospitalisation or prolongation of existing inpatients' hospitalisation
- results in persistent or significant disability or incapacity
- is otherwise medically important.

A SAE is defined as a *Suspected Serious Adverse Reaction* (SSAR) if it is:

- judged to be at least possibly related to the study product by investigator.
- expected (listed in the Summary of Product Characteristics).

A SAE is defined as a *Suspected Unexpected Serious Adverse Reactions* (SUSARs) if it is:

- judged to be at least possibly related to the study product by either investigator or sponsor, and
- unexpected (not listed in the SmPC).

The following events are not regarded as SAE:

- Hospitalisation that was already planned or anticipated before participation to the study.
- Any SAE occurred before vaccination.

However, prolongation of these hospitalisations due to complications or other aspects mentioned in the definition of an SAE must be handled as an SAE.

10.2 (Serious) Adverse Events handling

10.2.1 Recording of (S)AEs

In case of an SAE, the event will be transferred to the current Spontaneous Reporting System: the case will be entered in the Lareb database, and will be reviewed and processed as a regular report with the exception that it will not be forwarded to Eudravigilance.

10.2.2 SAE reporting

The content of filled questionnaires, including any reported non-serious and serious events, will be transferred electronically to Baxter Ltd on a weekly basis, after coding by a Lareb investigator.

Serious AEs are reported to Baxter within 2 business days or 4 calendar days if a weekend is included. Potential signals will be reported within 3 business days or within 5 calendar days if a weekend is included.

10.2.3 Follow-up of (S)AEs

All SAEs are followed by Lareb until they have abated, or until a stable situation has been reached. This will be done according the usual Lareb standards.

10.3 New relevant safety information

The investigator will inform the parents of the toddlers, the authorities including the National Public Health Institute responsible for the National Immunisation Programme, and the applicable manufacturers if anything occurs that may negatively affect the burden or risks of participation as foreseen in the research proposal. The study may be suspended pending further review by the Lareb Scientific Advisory Board, provided that suspension does not jeopardise the toddlers' health. Lareb will take care that parents of all participating toddlers are kept informed.

CHAPTER 11. ETHICAL CONSIDERATIONS

11.1 Basic principles and regulations

The study team must ensure that this study is conducted in full conformance with the principles of the 'World Medical Association Declaration of Helsinki' (18th WMA General Assembly, Helsinki, Finland, June 1964, with last amendments by the 64th WMA General Assembly, Fortaleza, Brazil, October 2013), ICH guidelines for Good Clinical Practice as appropriate to pharmaceutical products, and local legislation of the country in which the research is conducted, whichever affords the greater protection to the individual.

11.2 Ethics Committee

This protocol and any accompanying informational material provided to the parents of the toddlers, will be submitted to the applicable Ethics Committee by the investigator according to local legislation. The Ethics Committee will firstly decide whether the proposed study fulfills criteria that necessitates a full review according to the Netherlands law on Investigations in humans (WMO). If so, approval from the Ethics Committee must be obtained before starting the study. Approval should be documented in a letter to the investigator specifying the date on which the Ethics Committee met and granted the approval, the composition of the Ethics Committee, and version and date of all submitted documents. If a formal review is not required for this non-invasive, non-interventional questionnaire based study, the Ethics Committee is asked for a Waiver letter.

11.3 Informed Consent

Prior to study enrolment, no written informed consent is obtained from the parents of each toddler. Instead, based on the information in the letter and/or flyer, they report themselves to participate by giving their email adress, and by agreeing to the Lareb privacy policy.

11.4 Confidentiality of study data

The investigator is responsible for treating subject and study information as confidential. The investigator should ensure that the subject identity will not be made publicly available. All subject study records are identified only by the subject identification number to maintain subjects' confidentiality. Identification codes lists that link the subjects' names to the subjects' identification number must be stored in the Investigator Site File.

11.5 Benefits and risks assessment

No known or potential risks are expected from the use of the study products, other than those applicable for the national Immunisation Programme.

11.6 Incentives/Compensation for subjects

Neither parents nor toddlers will receive a financial or other compensation for their participation in the study.

11.7 Insurance

Not applicable.

CHAPTER 12. ADMINISTRATIVE ASPECTS AND PUBLICATION

12.1 Roles and responsibilities

During the study a study team will be available on telephone to assist parents in filling the questionnaires.

12.2 Source data

All information obtained during the study will be directly recorded in an electronic database. Manually coded entries from free text field can be verified.

12.3 Data handling

All study data are kept on the central Lareb server. Backups are made daily.

Investigators are mandated to

- edit data if they are redundant,
 - to code reactions according to MedDRA terminology from free text field
- A data trail is formed by logging any changes.

12.4 Criteria for premature termination of the study

The study may be terminated as signals arise that would make continuation unsafe. As the vaccines under study are in general use, such situation may also have consequences beyond the scope of the study and its participants.

